17.2.1. LABORATORY REFERENCE RANGES AND MARKEDLY ABNORMAL CRITERIA

Quantitative laboratory measurements will be compared with the relevant laboratory reference ranges in SI units and categorized as:

- Low: Below the lower limit of the laboratory reference range.
- Normal: Within the laboratory reference range (upper and lower limit included).
- High: Above the upper limit of the laboratory reference range.

Document:

Author:

Version Number:

V2.0

Version Date:

21MAY2020

Template No: CS_TP_BS016 Revision 4
Effective Date: 01Apr2016

Reference: CS_WI_BS005

For laboratory parameters with categorical outcomes, measurements will be compared with the relevant laboratory reference values and categorized as normal or abnormal.

In addition to the high and low quantitative laboratory assignments (as identified by means of the laboratory reference ranges), markedly abnormal quantitative safety (and other) laboratory assessments will also be identified in accordance with the predefined markedly abnormal criteria as presented in [APPENDIX 5](#).

17.3. ECG EVALUATIONS

Results from the central ECG will be included in the reporting of this study.

The following ECG parameters will be reported for this study:

- PR Interval (msec)
- RR Interval (msec)
- QRS Interval (msec)
- QT Interval (msec)
- QTcF Interval (msec) [derived]
- QTcB Interval (msec) [derived]
- Heart rate (HR) (beats/min)
- ECG findings
- Overall assessment of ECG (investigator's judgment):
 - Normal
 - Abnormal, clinically Significant (CS)
 - Abnormal, not clinically significant (NCS)

The following summaries will be provided for ECG data for the SAF population:

- By visit summary of observed values and changes from baseline (for quantitative measurements)
- By visit and overall (including unscheduled visits) summary of ECG overall assessment results. Percentage of subjects will be based on the number of subjects with ECG overall assessment available at the given time point. Any unscheduled ECG that occurs after first dose will be included in the overall post-treatment summaries.
- Shift in ECG overall assessments from baseline to Week 6.

Document:

Author:

Version Number:

V2.0

Version Date:

21MAY2020

Template No: CS_TP_BS016 Revision 4
Effective Date: 01Apr2016

Reference: CS_WI_BS005

- Number and percentage of subjects with QTc levels in each of the QTc categories

The number and percentage of subjects with QTc values in the following categories will be identified, same criteria apply to both QTcF and QTcB:

- ≥ 450 msec for males \ ≥ 470 msec for females at any postbaseline time point (including unscheduled visits) not present at baseline
- ≥ 480 msec for male or females at any postbaseline time point (including unscheduled visits) not present at baseline
- ≥ 500 msec for males or females at any postbaseline time point (including unscheduled visits) not present at baseline
- ≥ 30 msec and < 60 msec increase from baseline for at least one postbaseline measurement (including unscheduled visits)
- ≥ 60 msec increase from baseline for at least one postbaseline measurement (including unscheduled visits)

All ECG parameters, overall interpretation, and findings will be provided in data listings. A listing displaying ECG values for subjects with at least 1 prolonged QTc will be produced.

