13. TERMINATION OF SUBJECT FROM STUDY/ DISCONTINUATION OF STUDY DRUG

13.1. Criteria for Subject Termination

Subjects may terminate the study participation at any time for any reason.

The possible reasons for the termination of study participation are as follows:

- Adverse event.
- Lack of efficacy (specify).
- Lost to follow-up (specify).
- Pregnancy.
- Withdrawal by subject (specify).
- Non-compliance with study drug (specify).
- Protocol deviation (specify).
- Death
- Other (specify).

If at any time during the course of the study, in the opinion of the Investigator, the subject may no longer safely participate due to a change in medical status (eg, experiences an AE, becomes pregnant), the subject must be discontinued from the study drug.

Subjects who, at any study visit post-baseline have a QTcF value greater than 500 ms, who have a > 60 ms increase in QTcF from baseline, or who experience a life-threatening arrhythmia will be discontinued from the study drug and followed until the event resolves; in addition, an adverse event will be reported.

Subjects who develop adverse events of amenorrhea, gynecomastia, or galactorrhea are to be discontinued from the study drug. The reason for discontinuation and information on the epoch will be recorded on the appropriate CRF. In case of death, the date of death should be captured on the CRF.

Subjects who prematurely terminate the study participation will not be replaced.

Subjects who discontinue prior to Visit 6 (Day 42 [± 2]) will undergo procedures and assessments scheduled for Visit 6 (Day 42 [± 2]) at the time of early discontinuation (see [Section 11.6.3](#)).

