15.3.6.4. ECGs

All ECG summaries will be based on the Safety population. ECG parameters will include ventricular heart rate, PR interval (msec), RR interval (msec), QRS duration, QT interval, and corrected QT intervals (Bazett's QT_cB and Fridericia's QT_cF).

Summary statistics for the actual values and change from baseline will be presented by treatment group at each time point for each parameter.

Shifts from baseline will be produced by treatment group to show the number and percentage of subjects for changes in overall ECG assessments at post-baseline.

The number and percentage of subjects with elevated QTc intervals (> 450 msec for males, > 470 msec for females, > 480 msec and > 500 msec for males or females) and changes from baseline in QT_c intervals \geq 30 msec, but < 60 msec and \geq 60 msec will be summarized by treatment group. A listing displaying ECG values for subjects with at least one prolonged QT_c will also be produced.

For other ECG parameters, subjects will be classified as normal or abnormal (see SAP for details). For abnormal ECG parameter reporting, counts and percentages of subjects will be presented by treatment group.

For these categorical analyses, the percent of subjects will be based on the number of subjects with at least one non-missing post treatment value. Any early termination visit or unscheduled ECG that occurs after first dose will be included for these posttreatment summaries.

Electrocardiogram clinical interpretation of ECG findings will be presented in data listings.

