6.4. RETESTS, UNSCHEDULED VISITS AND EARLY TERMINATION DATA

In general, for by-visit summaries, data recorded at the scheduled visits will be presented.

Unscheduled measurements will not be included in by-visit summaries. Unscheduled measurements collected prior to the first dose of study drug will contribute to the derivation of the baseline value. Unscheduled measurements collected postbaseline will contribute to the derivation of markedly abnormal postbaseline value, and best/worst case value where required (eg, shift tables).

Early termination data collected postbaseline will be assigned to the next planned visit for that assessment as explained in [Section 6.3](#). This mapping will be implemented to all early termination data points used in the efficacy and safety analyses.

Listings will include scheduled, unscheduled (including retests), and early termination data with original dates and visits displayed.

Document:

Author:

Version Number:

V2.0

Version Date:

21MAY2020

Template No: CS_TP_BS016 Revision 4
 Effective Date: 01Apr2016

Reference: CS_WI_BS005

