17.2. LABORATORY EVALUATIONS

All summaries will be based on the SAF population. Laboratory data to be reported for this study include Hematology, Serum Chemistry (including lipid panel and thyroid panel), Urinalysis, Urine drug screening, Hemoglobin (HbA1c), serum follicle stimulating hormone (FSH), Serum Prolactin, Serology, Serum Insulin, C-Reactive Protein (CRP), and urine pregnancy test. A list of laboratory assessments to be included in the outputs is included in section 21 of the CSP. Urine drug screening, serum FSH, serology, and urine pregnancy test will only be listed.

Presentations will use international system of units (SI).

Quantitative laboratory measurements reported as “< X”, ie, below the lower limit of quantification (BLQ), or “> X”, ie, above the upper limit of quantification (ULQ), will be converted to X for the purpose of quantitative summaries, but will be presented as recorded, ie, as “< X” or “> X” in listings.

The following summaries will be provided for laboratory data:

- By-visit summary of observed values and changes from baseline for continuous data in hematology, chemistry, and urinalysis.
- By visit summary of the number and percentage of subjects in each outcome category for categorical data in urinalysis (if applicable).

Document:

Author:

Version Number:
Version Date:

V2.0

21MAY2020

Template No: CS_TP_BS016 Revision 4
Effective Date: 01Apr2016

Reference: CS_WI_BS005

- Shift in laboratory results (chemistry, hematology, urinalysis) from baseline to Week 6 according to the reference range criteria. The normal reference ranges from the central laboratory will be used to determine whether the laboratory test value is below, within, or above the normal range. Urinalysis will be presented as normal or abnormal (including low, high, abnormal) in the shift table.
- By planned visit (after mapping of the ET visit) and overall (including unscheduled visits) summary of markedly abnormal postbaseline value (MAPLV, see [Section 17.2.1](#) and [APPENDIX 5](#)). Subjects will be represented in the count of a particular MAPLV (potentially clinically significant [PCS] low or high) if they have experienced that MAPLV at least once postbaseline, regardless of baseline value. The number and percentage of subjects with MAPLV will be presented by treatment group.
- Shift in markedly abnormal laboratory results from baseline to postbaseline according to the markedly abnormal criteria as presented in [APPENDIX 5](#).

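### SAP 17.3 narrows the ECG overall-assessment shift to Week 6 without declaring it, so new non-QTc abnormalities before Week 6 can be missing from the shift table

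*SAP*

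**What the plan says.** - **Protocol 15.3.6.4 (ECGs)** wants shifts from baseline by treatment group that show the "number and percentage of subjects for changes in overall ECG assessments at post-baseline". It names no visit. Three paragraphs later, for what it calls these categorical analyses, it adds that "the percent of subjects will be based on the number of subjects with at least one non-missing post treatment value" and that "Any early termination visit or unscheduled ECG that occurs after first dose will be included for these posttreatment summaries".
- **SAP 17.3 (ECG Evaluations)** plans "Shift in ECG overall assessments from baseline to Week 6". The assessment is the investigator's three-level judgment: normal, abnormal not clinically significant, or abnormal clinically significant.
- **SAP 17.3** also plans a summary of the overall assessment by visit and overall, with unscheduled ECGs in the overall part. It counts subjects who cross QTc thresholds at any post-baseline time point when they had not done so at baseline, and subjects with QTc increases from baseline.
- **SAP 3.7 (Changes to Analysis from Protocol)** has one ECG entry, which makes the threshold inequalities inclusive. The shift table is not mentioned.
- **SAP 6.3, Table 1** assigns an early-termination ECG to the next planned visit, not automatically to Week 6.

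**The concern.** A shift table answers a specific safety question: how many subjects moved from a normal to an abnormal ECG on treatment. Fixing it at Week 6 limits it to subjects who reached Week 6, or came close enough for their last ECG to be mapped there, and to abnormalities still present then. An abnormality that was transient, or that came before early withdrawal, is not counted.

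The protocol's scope is wider, and a reader of the report would not learn of the narrowing from SAP 3.7. What is at stake is the completeness of one descriptive safety table. No efficacy result and no Type I error is involved.

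**Working it through.** The plan states no figure on this point, so the check compares texts and counts days.

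**1. Which early terminations reach the Week 6 ECG row (SAP Table 1)**

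| Early-termination study day | Analysis visit | Number of days | In the Week 6 shift? |
|---|---|---|---|
| 1-9 | Week 1 | 9 | No |
| 10-16 | Week 2 | 7 | No |
| 17-30 | Week 4 | 14 | No |
| 31-44 | Week 6 | 14 | Yes |

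Days that miss the table: 9 + 7 + 14 = 30, and 30/44 = 68%. Days that stay in: 14/44 = 32%.

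These are shares of calendar days, not of subjects. The documents give no distribution of withdrawal times. The share of early terminations that is lost could therefore be anything from 0% (all on Day 31 or later) to 100% (all by Day 30).

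The follow-up ECG does not fill the gap, because SAP Table 2 maps Visit 7 to Week 7.

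**2. How each kind of subject is treated**

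- A subject whose ECG turns abnormal at Day 7 or Day 14 and who leaves then is absent from the shift table.
- A subject whose ECG turns abnormal at Day 14 or Day 28 and is normal again at Day 42 is present, and is counted as no shift.
- A subject whose ECG turns abnormal and who leaves on Days 31-44 is present, with the shift counted.

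Three of the four on-treatment ECG visits in the Schedule of Assessments (Days 7, 14, 28 and 42) come before Week 6.

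**3. Whether another SAP 17.3 output supplies what is lost**

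| Output | Covers ECGs before Week 6? | Conditions on the subject's baseline? | Covers non-QTc abnormalities? |
|---|---|---|---|
| Overall-assessment shift | No | Yes | Yes |
| Overall-assessment summary, by visit and overall | Yes | No | Yes |
| QTc threshold and increase categories | Yes | Yes | No |

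Quantitative changes from baseline in PR, RR, QRS and heart rate are summarized by visit, but that is not a count of subjects who became abnormal. Protocol 15.3.6.4 leaves the normal/abnormal classification of the other ECG parameters to the SAP, but SAP 17.3.2 sets criteria only for QT, QTcB and QTcF. For abnormalities outside these intervals, the shift table is the only categorical ECG summary that uses the baseline reading.

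The baseline reading matters because subjects can enter with an abnormal overall assessment. Among other listed abnormalities, exclusion criterion 11 bars a non-sinus rhythm at Screening only when the investigator judges it clinically significant. In the unconditioned summary, pre-existing and new abnormalities are counted together.

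**The case against.** The other side has five good points.

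**The protocol wording is loose.** Post-baseline says neither any visit nor worst value. The denominator and early-termination sentences follow the QTc and other-parameter counts, so applying them to the shift table is an inference. This stands. Baseline-to-worst is a reasonable way to meet the protocol wording, not its literal text. Even so, an unrestricted post-baseline scope is not the same as Week 6, and the narrowing is undeclared.

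**The QTc signal is not hidden.** A reader might infer that subjects withdrawn under the QTcF rule in Protocol 13.1 vanish from the safety reporting. They do not. The QTc categories use any post-baseline ECG and condition on baseline, and prolonged-QTc subjects are listed. The protocol also requires an adverse event for these withdrawals, and for clinically significant ECG findings generally (Protocol 12.2). This stands, and it limits the point to non-QTc findings, chiefly those not reported as adverse events.

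**Not every withdrawal is lost.** Early terminations on Days 31-44 remain in the table, as the day count shows.

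**The laboratory tables are a different matter.** SAP 17.2 also sets its reference-range shift at Week 6, and a reader might infer the same conflict. The documents do not support that. Protocol 15.3.6.4 covers ECGs only, and Protocol 15.3.6.3 gives no time point for laboratory shifts. SAP 17.2 separately plans "Shift in markedly abnormal laboratory results from baseline to postbaseline according to the markedly abnormal criteria".

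**SAP 6.4 does not impose a worst-value rule.** It concerns unscheduled measurements and applies only where a best or worst value is required, with shift tables as an example. The markedly abnormal laboratory shift and the AIMS maximum-severity shift already give it something to act on. It is consistent with a worst-value ECG shift but does not require one.

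**Conclusion.** The point holds for the ECG overall-assessment shift. SAP 17.3 is narrower than Protocol 15.3.6.4, SAP 3.7 does not declare it, and no other planned categorical ECG summary shows new non-QTc abnormalities before Week 6 against the subject's own baseline.

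Its size is modest: one descriptive safety table is affected, and the main QTc outputs are intact. The number of subjects affected cannot be derived from the documents. They give neither withdrawal times nor ECG abnormality rates, and the only dropout figure is the 9 of 45 assumed for the Japanese cohort. A reader might infer that the loss would be greater in an arm with more cardiac effects. That is plausible, but nothing in the documents quantifies it.

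The conclusion assumes that a subject who terminates early has no later Week 6 visit. Protocol 13.1 supports this by bringing the Visit 6 procedures forward to the time of discontinuation. A subject who stopped the drug but still attended at Day 42 would remain in the table.

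**What to change.** In SAP 17.3, define the ECG overall-assessment shift as baseline to worst post-baseline assessment, ordered normal, abnormal not clinically significant, abnormal clinically significant. Include early-termination and unscheduled ECGs after first dose. Use as denominator the subjects with a baseline ECG and at least one post-dose ECG. State whether the Visit 7 follow-up ECG counts. Keep the Week 6 shift as an additional table.

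If the sponsor prefers Week 6 alone, the restriction should be listed and justified in SAP 3.7, although that would leave the gap for non-QTc findings.

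The cost is a few lines of SAP text and one more table from ECGs already scheduled for collection. The laboratory shift tables need no change on this ground.

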17.3.1. ECG SPECIFIC DERIVATIONS

The following 3 measures are provided by the ECG vendor and those provided values will be analyzed. If one of these values is missing and derivation in the course of analysis is needed, the following derivations may be used:

- Bazett's Correction of QT interval (msec)

$$QTcB \text{ (msec)} = \frac{QT \text{ (ms)}}{\sqrt{RR \text{ (ms)}}/1000}$$

- Fridericia's Correction of QT interval (msec)

$$QTcF \text{ (msec)} = \frac{QT \text{ (ms)}}{\sqrt[3]{RR \text{ (ms)}}/1000}$$

- RR Interval – If RR Interval is not available it will be derived from HR as follows, for the derivation of the QTc corrections

$$RR \text{ (msec)} = 1000 * \frac{60}{HR \text{ (bpm)}}$$

17.3.2. ECG MARKEDLY ABNORMAL CRITERIA

Document:

Author:

Version Number:

V2.0

Version Date:

21MAY2020

Template No: CS_TP_BS016 Revision 4
Effective Date: 01Apr2016

Reference: CS_WI_BS005

Markedly abnormal quantitative ECG measurements will be identified in accordance with the following predefined markedly abnormal criteria:

- Absolute values for QT interval, QTcB interval and QTcF will be classified as:
 - >= 450 msec for males \ >= 470 msec for females
 - >= 480 msec for males or females
 - >= 500 msec for males or females
- Change from Baseline for QT interval, QTcB interval and QTcF will be classified as:
 - >= 30 msec and < 60 msec increase from baseline
 - >= 60 msec increase from baseline

17.4. VITAL SIGNS

The following vital signs measurements will be reported for this study:

- Supine Systolic Blood Pressure (mmHg)
- Standing Systolic Blood Pressure (mmHg)
- Supine Diastolic Blood Pressure (mmHg)
- Standing Diastolic Blood Pressure (mmHg)
- Supine Pulse Rate (beats/min)
- Standing Pulse Rate (beats/min)
- Respiratory Rate (breaths/min)
- Temperature (C)
- Weight (kg)
- BMI (kg/m²)
- Waist circumference (cm)

The following summaries will be provided for vital signs data for the SAF population:

- Observed value and change from baseline by visit including the follow-up visit.
- BMI Categories will be described by visit.

Document:

Author:

Version Number:
Version Date:

V2.0

21MAY2020

Template No: CS_TP_BS016 Revision 4
Effective Date: 01Apr2016

Reference: CS_WI_BS005

- Mantel-Haenszel row mean scores test will be used to compare each SEP-4199 group and placebo similar to the laboratory parameters.
- By visit and overall summary of Markedly Abnormal Postbaseline Vital Signs (MAPVS, see [Section 17.4.1](#)). This analysis will include only subjects having experienced MAPVS at least once postbaseline.
- The number and percentage of subjects with orthostatic hypotension and orthostatic tachycardia will be summarized by treatment for baseline and the overall postbaseline period, as well as by visit. As specified in [Section 6.3](#), any orthostatic hypotension or tachycardia events that occurred at the early termination visit will be assigned to the next planned visit. Orthostatic hypotension is defined as a decrease of ≥ 20 mmHg in systolic blood pressure or ≥ 10 mmHg in diastolic blood pressure after the subject had been standing for at least 2 to 4 minutes, compared to the systolic and diastolic blood pressures measured in the supine position, respectively. Orthostatic tachycardia is defined as a heart rate increase of at least 20 beats per minute (bpm) after the subject was standing for at least 2 to 4 minutes, compared to the heart rate measured in the supine position and a heart rate > 100 bpm after the subject was standing for at least 2 to 4 minutes. Standing vital signs will be used as collected on the CRFs.

All vital signs data will be provided in a data listing, including flagging of MAPVS.

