15.3.6.5. Vital Signs

All vital sign summaries will be based on the Safety population.

Summary statistics for actual values and the change from baseline will be presented by treatment group, for each time point and each parameter.

Nonparametric rank ANCOVA with adjustments for baseline value will be applied to change from baseline in weight and BMI for comparison between each SEP-4199 group and placebo.

The number and percentage of subjects with Markedly Abnormal Post-baseline Vital Signs (MAPVS, defined in the SAP) will be presented at each post-baseline visit and overall. Included will be subjects having experienced MAPVS at least once post-baseline.

The number and percentage of subjects with orthostatic hypotension and orthostatic tachycardia will be summarized by treatment by time point and overall. Orthostatic hypotension is defined as a decrease of ≥ 20 mmHg in systolic blood pressure or ≥ 10 mmHg in diastolic blood pressure after the subject had been standing for at least 2 to 4 minutes, compared to the systolic and diastolic blood pressures measured in the supine position, respectively. Orthostatic tachycardia is defined as a heart rate increase of at least 20 beats per minute (bpm) and a heart rate > 100 bpm after the subject was standing for at least 2 to 4 minutes, compared to the heart rate measured in the supine position.

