17.4.1. VITAL SIGNS MARKEDLY ABNORMAL CRITERIA

MAPVS measurements will be identified in accordance with the following predefined markedly abnormal criteria:

Table 5. Markedly abnormal vital sign criteria.

Parameter Name	Low	Decrease from Baseline	High	Increase from Baseline
Systolic BP	≤ 90 mmHg	≥ 20 mmHg	≥ 180 mmHg	≥ 20 mmHg
Diastolic BP	≤ 50 mmHg	≥ 15 mmHg	≥ 105 mmHg	≥ 15 mmHg
Pulse rate	≤ 50 bpm	≥ 15 bpm	≥ 120 bpm	≥ 15 bpm
Respiration Rate	≤ 10 breaths/min	$\geq 50\%$	≥ 25 breaths/min	$\geq 50\%$
Temperature	N/A		≥ 38.3 °C	≥ 0.8 °C increase from baseline

Note: A vital sign measurement is MAPVS Low if it is below the specified lower limit and decreased from baseline or MAPVS High if it is above the specified upper limit and increased from baseline.

Document:

Author:

Version Number:

V2.0

Version Date:

21MAY2020

Template No: CS_TP_BS016 Revision 4
 Effective Date: 01Apr2016

Reference: CS_WI_BS005

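### The rule for markedly abnormal vital signs limits the analysis to subjects who had the event, and the note under SAP Table 5 does not match the table's limits

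*SAP*

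**What the plan says.** SAP 17.4 opens its list of outputs with "The following summaries will be provided for vital signs data for the SAF population". One item is a summary of MAPVS by visit and overall, and it ends: "This analysis will include only subjects having experienced MAPVS at least once postbaseline". MAPVS are also flagged in the vital-signs listing.

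Protocol 15.3.6.5 asks for the same output, by visit and overall: "The number and percentage of subjects with Markedly Abnormal Post-baseline Vital Signs". The sentence after that request is: "Included will be subjects having experienced MAPVS at least once post-baseline". It leaves the definition of MAPVS to the SAP.

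SAP 17.4.1, Table 5, gives most parameters a limit and a change from baseline, both inclusive:
- systolic pressure: low ≤ 90 mmHg with a decrease ≥ 20 mmHg; high ≥ 180 mmHg with an increase ≥ 20 mmHg
- diastolic pressure: low ≤ 50 mmHg with a decrease ≥ 15 mmHg
- pulse: low ≤ 50 bpm with a decrease ≥ 15 bpm

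The note beneath reads: "A vital sign measurement is MAPVS Low if it is below the specified lower limit and decreased from baseline". It gives the mirror image for High.

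Two parallel rules are useful for comparison. For markedly abnormal laboratory values, SAP 17.2 makes one or more occurrences after baseline a counting rule: "Subjects will be represented in the count of a particular MAPLV (potentially clinically significant [PCS] low or high) if they have experienced that MAPLV". Protocol 15.3.6.4 says of the categorical ECG analyses that "the percent of subjects will be based on the number of subjects with at least one non-missing post treatment value".

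**The concern.** There are two separate faults.

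First, the sentence in 17.4 defines who is in the analysis by the event the analysis is meant to count. A percentage computed on that set says nothing about how often MAPVS occurred in an arm, so the arms cannot be compared on it.

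Second, Table 5 and its note are the only definition of MAPVS in either document, and they disagree at the limit value. The note also mentions a change from baseline without giving its size. Two programmers working from this text could flag different subjects.

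At stake is one descriptive safety table and the matching listing flags. The primary analysis, the type I error and the power are untouched.

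**Working it through.** **No planned figure to reproduce.** Neither document gives an MAPVS rate, count or denominator.

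**Denominator.** Let k be the number of subjects in an arm with at least one MAPVS after baseline, and take the planned US/Europe arm size of 98 as an illustrative denominator.
- Literal reading: k/k. This is 1/1, 3/3 or 9/9 = 100% each time, and 0/0 (undefined) in an arm with no case.
- Numerator reading: k/98. This is 1/98 = 1.0%, 3/98 = 3.1% and 9/98 = 9.2%.

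Only the overall any-MAPVS row is forced to 100% on the literal reading. By-visit and single-parameter rows become shares of the cases, which can fall below 100% but are still not rates among treated subjects.

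**Table against note, low systolic pressure.**
- A fall from 110 to 90 mmHg: 90 ≤ 90 meets the table's limit and the fall of 20 meets its change. The note requires a value below 90, so it fails there whatever size of change the note intends. This is a plain contradiction.
- A fall from 92 to 89 mmHg: 89 is below 90 and the value has decreased, so it counts if the note is taken word for word. The fall is 3, short of the tabulated 20, so it does not count if the note is shorthand for the table's two columns. This is an ambiguity.

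**Effect on counts.** The documents give no vital-sign means, SDs, within-subject correlation or rounding habits, so everything here is assumed: normal readings, exchangeable correlation 0.40 to 0.75, one baseline and 5 post-baseline readings, no drug effect, 200,000 simulated subjects per setting. Mean and SD ranges were systolic 115–125 and 11–14, diastolic 72–78 and 8–10, pulse 70–75 and 9–11. Two rules were compared on subjects ever flagged low: the table (at or below the limit and at least the tabulated decrease) and the note word for word (below the limit and any decrease). High values were not simulated.

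Ratio of subjects flagged, note divided by table, as range (median):

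| | Whole-number readings | 30% of readings rounded to nearest 10 |
|---|---|---|
| Systolic | 1.19–10.4 (2.2) | 0.50–3.6 (1.2) |
| Diastolic | 0.95–8.2 (1.9) | 0.25–2.3 (0.7) |
| Pulse | 1.15–6.4 (2.0) | 0.49–2.7 (1.1) |

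With whole-number readings, the boundary alone (inclusive over strict, same required decrease) gives a ratio of 1.12 to 1.67. The size of decrease alone (any decrease over the tabulated one, at the inclusive limit) gives 1.4 to 12.8. The two act in opposite directions: the strict limit removes subjects and the missing size of change adds them. Rounding to the limit values therefore can reverse the net effect.

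**The case against.** The strongest defence is that the sentence in 17.4 merely paraphrases the protocol's "Included will be subjects having experienced MAPVS at least once post-baseline". In the protocol that sentence follows directly on a request for a number and percentage, so it says who is counted. The laboratory rule uses the same at-least-once idea openly as a counting rule. The SAF population is named for the vital-signs list and for all safety outputs, and SAP 3.7 lists no change to MAPVS from the protocol. The table templates cited in SAP 8 are not part of the documents and may state a denominator. As for the note, Table 5 does not itself say how its columns combine; the note is the only text that joins them, and reading it as limit plus tabulated change gives the change columns a purpose.

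Much of this stands. A numerator rule is probably what was meant, and on the size of change the note is ambiguous rather than contradictory. A reader might infer that every arm will show 100%. The documents do not support that: it needs the literal reading, an arm with at least one case, and the overall any-MAPVS row.

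Three things survive. The SAP added the word *only* and made the analysis the subject of the sentence, so its text is further from a counting rule than the protocol's. The MAPVS denominator is stated nowhere, although the protocol states one for ECG. And the mismatch between strict and inclusive limits remains under every reading. The sponsor treats such a boundary as worth recording: SAP 3.7 logs a change from > to ≥ for the ECG categories.

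**Conclusion.** The point holds as a minor correction. Followed literally, SAP 17.4 gives an overall any-MAPVS percentage of 100% in any arm with a case and an undefined one in an arm without. The probable intent is otherwise, but nothing in either document states the denominator. The Table 5 note contradicts the table at the limit value and leaves the required size of change open.

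A reader might also infer that choosing the note over the table roughly doubles the low-value counts. The documents do not support any such figure. A ratio near 2 is only the median under one set of assumed inputs with whole-number readings. Over all the inputs tried it runs from about 0.25 to 10, and the direction can change. What can be said is that the counts depend on which rule is coded.

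Nor is this the whole vital-signs safety assessment: SAP 17.4 also plans observed values and changes by visit, and counts of orthostatic hypotension and orthostatic tachycardia. The consequence is confined to one descriptive table and its listing flags.

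**What to change.** Make two replacements in the SAP.

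- **Section 17.4, last sentence of the MAPVS item:** the denominator is SAF subjects with a baseline and at least one post-baseline value of the parameter (for by-visit rows, a value at that visit). A subject is counted once overall if MAPVS occurred at least once after baseline.
- **Note to Table 5:** MAPVS Low (High) requires both the Low (High) limit, inclusive as tabulated, and the Decrease (Increase) from baseline shown in the table.

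Requiring a baseline value follows from the definition, since MAPVS cannot be judged without a change from baseline. The wording keeps the table's own values and introduces no new threshold. The table and the listing flags should be programmed from this single definition. The cost is two sentences, with no new data and no effect on the efficacy analyses.
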